8.2.5 Storage and Stability

Vials of CDX-1140 are shipped in insulated shippers and must be stored at ≤ - 65°C (-85°F) until use and protected from light – storage at -85°F will be done by the primary investigators. The day of treatment, CDX-1140 can be stored at room temperature for up to 3 hours, or refrigerated (at 2-8 degrees) for up to 6 hours if necessary.

8.2.6 Administration

Each vial to be used for intravenous administration contains a premixed solution, containing 3.0 mg/mL CDX-1140 protein in a 10.0 mL volume of buffered solution. Injections can be performed through any standard IV method (peripheral IV, PICC, PORT, or any other IV access that is in place or most convenient for the patient). Patients should be given CDX-1140 IV once per month.

8.2.7 Special Handling Instructions

No special handling instructions.

9 CORRELATIVE STUDIES

9.1 Fresh Tumor Tissue

9.1.1 Collection of Specimen

Tumor tissue will be collected at the time of surgical resection. Tissue received from the OR is brought to the pathology processing table. At this point, the tissue is sectioned and "bread loaved" by a pathologist. Current best practice for correlative studies will take a central plane cross-section from the tumor if not interfering with clinical pathological assessments. Tumor tissue will then be transported to the research labrotory on wet ice in DMEM media. A smaller portion (~20% of available biomarker tissue) will directly cryopreserved in liquid N2 or on dry ice.

Processing labrotory is located at BJCIH 7th floor, room 7202 ([name]-lab).

9.1.2 Handling of Specimen(s)

Tumor tissues will be divided into two pieces. Twenty percent of tissue will be directly cryopreserved in liquid N2 or on dry ice, while eighty percent of the tissue will be placed in DMEM Media in wet ice. Samples will be transported on wet and dry ice to the research labrotory for processing. Research processing laboratory is located at BJCIH 7th floor, room 7202 ([name]-lab).

9.2 Archived Tumor Tissue

Archival tissue will be retrieved from pathology thru the SCC request system. This will also be used to inspect potential sampling biases or problems.

9.3 Research Blood

Blood will be collected at three time points:

- At screening
- Prior to first therapeutic dose of CDX-1140, on the day of infusion

• At the time of surgery.

For each blood collection three 10ml green-top (sodium heparin) tubes will be collected for PBMCs and plasma along with one red-top sera (no-anticoagulant) tubes. Samples will be transported on wet ice to the research laboratory for processing.

Processing laboratory is located at BJCIH 7th floor, room 7202 ([name]-lab).

Additionally, no more than 10 mL of blood will be collected at any standard follow-up visit to analyze for CDX-301 ADAs. This blood will be collected in to a single red top tube, labeled with patient ID, date, and visit time point, and will be taken directly to the [name] lab for cryopreservation and batch shipping to Celldex.

9.4 Specimen Analysis

First, we will assess the impact of CDX-1140 compared to CDX-301/CDX-1140 on multiple parameters of PDAC local and systemic tumor immunity. Second, we expect diverse objective responses to therapy; blood and PDAC tissues parameters can be correlated with patient outcomes to identify the biological parameters that indicate therapeutic benefit.

Our tissue collections will include pre- treatment and time of surgery blood and sera, as well as tumor tissue collected at the time of surgery. Tissue collection will be mandatory for all patients. Tumor tissues will be divided into cryopreserved, formalin-fixed paraffinembedded (FFPE), and flow cytometry/CyTOF samples. We will directly assess how notreatment vs CDX-1140 vs CDX-301/CDX-1140 alters immune cell tumor infiltration using high-density flow cytometry and CyTOF. We optimized two 14-parameter flow cytometry protocols to assess T-cell infiltration, activation, and exhaustion, and myeloid cell and DC infiltration and two 35 parameter CyTOF panel (see **Figure**). This will be complemented by Single Cell RNA sequencing when tissue it sufficient. Conventional dendritic cells are defined by the lack of expression of CD3, CD19, CD20, CD16, CD56, and the expression of CD45, CD11c, MHCII high and either CD1c or CD141.

On archival FFPE tissues we will complement flow cytometry with multiplex IHC on FFPE tissue. We optimized several multiplex IHC panels using the PerkinElmer OPAL system. These panels can identify changes in T-cell infiltration and proliferation (e.g., CD3⁺/CD8⁺/Ki67⁺) and proximity to tumor cells (CK19). For imaging and deconvolution we will capture images and conduct quantitative analysis using HALO pattern recognition software.

We will analyze blood leukocyte populations using two optimized 36-parameter CyTOF panels designed for adaptive and innate immune cells, respectively. We will focus on evidence of increased T-cell activation corresponding with tumor reactivity (similar to results from human checkpoint studies^{43, 44}). This will include analyses of T-cell proliferation (Ki67), lineage transcription factors (e.g., GATA3, T-bet, Eomes), effector function (Granzyme B, perforin), memory status (e.g., KLRG1, CD28, CD127), exhaustion/checkpoint marker expression (e.g., 41BB, LAG3, TCF1 and SLMF6). We will perform unguided analysis of this CyTOF data using PhenoGraph and X-Shift to identify uniquely changing T-cell subsets, and Citirs to determine potential biomarkers of treatment response.

Α	Human CyTOF T Cell Pannel				
	Marker	Metal	Marker	Metal	
	CD45	089Y	CCR7	159Tb	
	open	115In	CD39	160Gd	
	CCR6	141Pr	Tbet	161Dy	
	CD19	142Nd	FoxP3	162Dy	
	ICOS	143Nd	BTLA	163Dy	
	CD38	144Nd	GITR	164Dy	
	CD4	145Nd	CD16	165Ho	
	IgD	146Nd	CD24	166Er	
	RORgt	147Sm	Gata3	167Er	
	PD-L1	148Nd	CD8	168Er	
	open	149Sm	IL-2R	169Tm	
	CD27	150Nd	CD3	170Er	
	CD14	151Eu	GranzymeB	171Yb	
	CTLA-4	152Sm	Ki67	172Yb	
	TIGIT	153Eu	CXCR4	173Yb	
	TIM-3	154Sm	PD-1	174Yb	
	CD45RA	155Gd	Perforin	175Lu	
	CXCR3	156Gd	NCAM	176Yb	
	CCR4	158Gd	CD11b	209Bi	
B PhenoGraph on α/β T Cells PDAC Tissues TH CTLs TReg					
TSNE-1 Figure. (A) T-cell CyTOF panel (B) CyTOF data from human PDAC					

subsets by PhenoGraph.

10 DATA SUBMISSION SCHEDULE

Case report forms with appropriate source documentation will be completed according to the schedule listed in this section.

Case Report Form	Submission Schedule	
Original Consent Form	Prior to registration	
On-Study Form	Drien to starting treatment	
Medical History Form	Prior to starting treatment	
Toxicity Form	Continuous	
Treatment Summary Form	Completion of treatment	
Surgery Form	Time of surgery	
Research Specimen Form	Baseline, time of CDX-1140 treatment, time of surgery	
Follow Up Form	Every 6 months for 2 years; 60 days after EOT if surgery	
	is not performed	
Progression Form	Time of disease progression	
Death Form	Time of death	
MedWatch Form	See Section 7.0 for reporting requirements	

10.1 Adverse Event Collection in the Case Report Forms

All adverse events that occur beginning with start of treatment (minus exceptions defined in Section 7.0) must be captured in the Toxicity Form. Baseline AEs should be captured on the Medical History Form.

Participant death due to disease progression should be reported on the Toxicity Form as grade 5 disease progression. If death is due to an AE (e.g. cardiac disorders: cardiac arrest), report as a grade 5 event under that AE. Participant death must also be recorded on the Death Form.

11 MEASUREMENT OF EFFECT

Primary Endpoint: This study is powered to detect a two-fold change in intratumoral conventional dendritic cells between CDX-1140 vs. CDX-301 plus CDX-1140 treated patients. This is a critical endpoint to ensure CDX-301 plus CDX-1140 is having its intended biological effect and thus has a likelihood of impacting tumor immunity and patient outcomes.

Correlative Secondary Endpoints: These will include global immune profiling by CyTOF, single cell RNASeq analysis, and histologic assessments. Critical to this assessment will be comparative analysis of the impact of CDX-1140 vs. CDX-301 plus CDX-1140 on T cell and cDC number and phenotype.

Exploratory endpoints: These will include local control rate, distant metastasis-free survival (DMFS), overall survival (OS), and margin negative resection rate. Proportions of local control and margin negative resection for all treated patients.

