1.2.6 Pancreas Cancer-Specific Studies with CDX-301 and CDX-1140

Mobilizing cDCs into early pancreatic lesions can reverse fibro-inflammatory responses

We tested if increasing cDCs in early stages of PDAC could reassert $T_{\rm H}1$ and CTL-mediated disease control. To accomplish this, we stimulated hematopoietic mobilization of cDC precursors using Fms-related tyrosine kinase 3 ligand (Flt3L) treatment $^{35\text{-}37}$. Flt3L administration at early stages of tumorigenesis resulted in robust infiltration of cDCs in the pancreas, including a 10-fold increase in cDC1s and revert disease acceleration and fibro-inflammatory pathology of PDAC in mice. Flt3L treatment also resulted in reduced number of pathogenic ROR- γ t⁺ IL-17A-expressing $T_{\rm H}$ cells and increases in IFN- γ -producing $T_{\rm H}1$ cells. Flt3L treatment increased CD8⁺T cell, proximity to lesions, effector function as measured by IFN- γ ⁺ and TNF- α ⁺ production, and proliferation. Together these data imply that restoring cDC numbers in early stages of PDAC results in a switch from pathogenic tumor-promoting $T_{\rm H}1$ 7 to tumor-restraining $T_{\rm H}1$ and CD8⁺ CTL responses to neoantigens.

Enhancing cDC infiltration and activation in advanced PDAC leads to disease stabilization

Our observations raised the possibility that Flt3L-based cDC mobilization in established pancreatic tumors could benefit anti-tumor immunity. Additionally, our previous work has shown that established PDAC in human patients and mouse PDAC models can impair cDC1 development in the bone marrow ³⁶ and therapeutic strategies might require boosting cDC mobilization to overcome this disruption. Thus, we treated PDAC bearing mice bearing advanced tumors with Flt3L. Notably, increases in cDC infiltration upon Flt3L treatment were more modest in established PDAC compared to premalignant pancreas and in this advanced setting FLT3L alone did not change intratumoral CTL infiltration.

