13.2 Sample Size Calculation

The primary endpoint is intratumoral conventional dendritic cells (cDCs) at surgery. The sample size calculation is based on the primary endpoint only. Our pilot data in animal models showed that the mean and standard deviation of the number of intratumoral cDCs per gram of tissue in CD40 agonist IgGs was 44726 with a standard deviation of 37895, and for mice treated with CDX-301 plus CD40 agonist, the mean cDCs per gram of tissue was 2716742 with a standard deviation of 1322448. Assuming a similar therapeutic effect on cDCs and similar distribution among samples, 12 patients per arm will have at least 99.9% power to detect the intratumoral cDCs difference as measured by CyTOF between two arms using a two-sided two-group T-test at the type I error of 5%. We plan to enroll 12 patients evaluable for the primary objective per arm for a total of 24 evaluable patients. An interim analysis can be performed at 5 patients per arm or greater; 5 patients per arm will have >80% power to detect changes in cDCs.

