13.4.4 Endpoint Analysis

The primary endpoint is intratumoral cDCs in surgical tissues. Conventional dendritic cells are defined by the lack of expression of CD3, CD19, CD20, CD16, CD56, and the expression of CD45, CD11c, MHCII high and either CD1c or CD141. Kruskal-Wallis test will be used to compare the difference between two

arms.

Exploratory endpoints include global immune profiling by CyTOF, single cell RNASeq analysis, and histologic assessments. Kruskal-Wallis test will be used to compare the difference on T cell and cDC number and phenotype between two arms.

Additional exploratory endpoints include local control rate, distant metastasis-free survival (DMFS), overall survival (OS), and margin negative resection rate. Proportions of local control and margin negative resection for all treated patients and their associated 95% confidence intervals will be calculated assuming a binomial distribution. Chi-square or Fisher's exact test will be used to compare the difference between two arms.

OS is defined as the time from the date of treatment to the date of death, censored at the last follow-up otherwise. DMFS is defined as the time from treatment to the date of distant metastasis or death, whichever occurs first. The alive patients without distant metastasis is censored at the last follow-up. The Kaplan-Meier method will be used to calculate the probability of OS and DMFS. The log-rank test will be considered to compare the difference of OS and DMFS between two arms.

Data on the toxicity in each arm will be collected for each subject, including frequency, type, and severity of adverse events. All analyses will be conducted using SAS (SAS Institute, Cary, NC) at the two-sided 5% significance level.

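### Section 11 claims power for a two-fold change in intratumoral cDCs, but the only power calculation is for a 60.7-fold difference seen in mice

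*Combined protocol and SAP*

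**What the plan says.** Section 11 (Measurement of Effect) attaches no condition, variability or power level to its statement: "This study is powered to detect a two-fold change in intratumoral conventional dendritic cells between CDX-1140 vs. CDX-301 plus CDX-1140 treated patients".

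Section 13.2 contains the only power calculation. Its inputs are animal data. For the CD40 agonist alone, the cDC count per gram "in CD40 agonist IgGs was 44726 with a standard deviation of 37895". For the combination, "the mean cDCs per gram of tissue was 2716742 with a standard deviation of 1322448". Assuming a similar effect and distribution in patients, and a two-sided two-group t-test at 5%, it concludes that "12 patients per arm will have at least 99.9% power to detect the intratumoral cDCs difference as measured by CyTOF between two arms". For an optional interim look it adds that "5 patients per arm will have >80% power to detect changes in cDCs", without naming an effect size.

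Section 13.4.4 gives the primary analysis as a test only: "Kruskal-Wallis test will be used to compare the difference between two" arms. Its confidence intervals belong to other endpoints: "Proportions of local control and margin negative resection for all treated patients and their associated 95% confidence intervals will be calculated".

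The other cDC fold changes in the documents are in Section 1.2.6. They are mouse cDC1 results: Flt3L alone in early lesions ("including a 10-fold increase in cDC1s") and a more than 64-fold increase with the combination in advanced tumours. Neither is a two-fold target.

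**The concern.** Saying that a study is powered for an effect is a statement about its operating characteristics. It needs an effect, a variability, a test, an alpha and a power. Section 11 supplies only the effect, and the one calculation elsewhere uses an effect about thirty times larger (60.7 / 2 = 30.4). High power for a 60-fold difference does not carry over to a two-fold one.

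What is at stake is how a null result is read. Section 11 presents this endpoint as the check that adding CDX-301 has its intended biological effect. A reader who takes two-fold as the effect the trial was sized for may treat a non-significant p-value as evidence against a doubling. Because the primary analysis has no interval estimate, no planned output would correct that reading by showing which fold changes remain possible.

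**Working it through.** **Inputs.** Means, SDs, 12 and 5 per arm, two-sided 5% and the t-test come from Section 13.2; 1:1 allocation from Section 13.1; the Kruskal-Wallis test from Section 13.4.4. The documents give no human SD or CV. The two-fold results therefore assume that human CVs equal the mouse CVs.

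**1. Effect and variability in Section 13.2**
- Ratio of means: 2,716,742 / 44,726 = 60.74.
- CV, CD40 agonist alone: 37,895 / 44,726 = 0.847.
- CV, combination: 1,322,448 / 2,716,742 = 0.487.

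**2. The plan's own figures**
- Difference: 2,716,742 − 44,726 = 2,672,016.
- Pooled SD: √[(37,895² + 1,322,448²)/2] ≈ 935,496, so d = 2.856.
- Power comes from the noncentral t with 2n − 2 df and noncentrality d√(n/2).
- n = 5: 2.856 × √2.5 = 4.52, power 97.6%.
- n = 8: 2.856 × √4 = 5.71, power 99.96% (n = 7 gives 99.83%).
- n = 12: 2.856 × √6 = 7.00, power 99.9999%.

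Both stated figures (at least 99.9% at 12, more than 80% at 5) reproduce for the mouse difference. Kruskal-Wallis power for that difference is about 100% at both sizes, so sizing by t-test and analysing by ranks does not alter them. The calculation passes 99.9% at 8 per arm (9 per arm with the Welch version), so it does not explain the choice of 12 or of two-fold.

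**3. Two-fold by the plan's t-test, by-arm CVs**
- Set the means to 1 and 2. The SDs are 0.847 and 2 × 0.487 = 0.974.
- Pooled SD: √[(0.847² + 0.974²)/2] = 0.913, so d = 1/0.913 ≈ 1.096.
- n = 12: noncentrality 1.096 × √6 = 2.68, power 72.8%.
- n = 5: power 33.3%.

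**4. Two-fold by the planned Kruskal-Wallis test**

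Data were simulated as lognormal with log-SD = √ln(1 + CV²), that is 0.735 and 0.461, using 200,000 replicates. When the arms have different CVs, a ratio of means is not a ratio of medians: mean ratio = median ratio × √(1 + 0.487²)/√(1 + 0.847²) ≈ 0.85 × median ratio. Both readings of two-fold are shown.

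| CVs assumed | t-test, 12/arm | Kruskal-Wallis, 12/arm | t-test, 5/arm | Kruskal-Wallis, 5/arm |
|---|---|---|---|---|
| By arm, mean ratio 2 | 72.8% | 88.5% | 33.3% | 49.2% |
| By arm, median ratio 2 | – | 73.0% | – | 35.8% |
| 0.487 in both | 86.0% | 93.0% | 44.0% | 55.1% |
| 0.847 in both | 41.6% | 58.1% | 18.1% | 26.8% |

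For CVs found nowhere in the documents, taken only to show sensitivity, Kruskal-Wallis power at 12 per arm is 99.7% at CV 0.35, 48% at 1.0 and about 31% at 1.5.

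**5. Fold change detectable with 80% power, by-arm CVs**
- 12 per arm: 2.13 (t-test); 1.81 as a mean ratio or 2.13 as a median ratio (Kruskal-Wallis).
- 5 per arm: 4.11 (t-test); 3.04 or 3.58 (Kruskal-Wallis).

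**6. What an interval would show.** A Hodges-Lehmann 95% interval on log cDC per gram with 12 per arm has a median half-width, as a factor, of 1.71 at the by-arm CVs. It is 1.50 with CV 0.487 in both arms and 1.90 with 0.847 in both.

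**The case against.** The best reply is that nothing is strictly contradicted. Power of 99.9% for a huge effect is compatible with good power for a smaller one, and Section 13.2 does not call 60-fold the smallest effect of interest. Section 13.2 also assumes that patients will be distributed as the mice were. On that assumption the planned test has 73% to 89% power for two-fold and reaches 80% between 1.81- and 2.13-fold. The implied miss rate of roughly 11% to 27% brackets the conventional 20%. This much stands: the claim may be near the truth, and the low power figures at CVs of 1.0 and 1.5 rest on values the plan never gives.

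It does not rescue the sentence. Whether it is true depends on a CV the plan does not state, and the plan's own t-test with its own CVs falls short of 80%.

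A second reply is that the 8-per-arm observation depends on pooling variances that are very unequal. Welch needs 9, which leads to the same inference. Using the larger SD in both arms gives 79.8% at 5 per arm and 99.7% at 12 by t-test, just short of both stated figures, so that reading does not explain them either.

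Third, the interim sentence follows the mouse assumption and makes no two-fold claim. That is correct; its fault is only that it names no effect size.

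Finally, the missing interval estimate can be called a separate matter. It is linked here because the interval would stop a null result from being misread against the two-fold statement.

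**Conclusion.** The concern holds. The two-fold statement in Section 11 is not derived anywhere in the documents. Section 13.2 is arithmetically correct, but for a 60.7-fold difference. With human CVs equal to the by-arm mouse CVs, a two-fold effect has 73% power at 12 per arm by the t-test. Under lognormal data the Kruskal-Wallis test has 73% (ratio of medians) to about 89% (ratio of means). Applying either mouse CV to both arms widens the range to 42% to 93%. At 5 per arm two-fold power is 18% to 55% over the same choices.

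This does not show that 12 per arm is inadequate, because the human variability is unknown. It should be fixed: the sentence describes the primary endpoint, and as written it can mislead the reading of a null result.

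**What to change.** 1. **Section 11.** Delete the two-fold powering sentence, or replace it with one target fold change (stated as a ratio of means or of medians), the assumed human CV, and the Kruskal-Wallis power at 12 per arm. As an illustration, if human CVs equal the by-arm mouse CVs, 12 per arm gives 83% power for a 2.2-fold ratio of medians.
2. **Section 13.2.** State the roughly 60-fold mouse effect beside both the 99.9% and the more-than-80% figures, and give power for the rank test that will be used.
3. **Section 13.4.4.** Alongside the test, report the between-arm cDC ratio with a 95% confidence interval, for example Hodges-Lehmann on log cDC per gram. At the by-arm mouse CVs and 12 per arm it would run from about the estimate divided by 1.7 to the estimate times 1.7.

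The cost is wording in three sections, one short simulation and one added estimate. The stated power will look less favourable. Sample size and primary test do not change.

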12 DATA AND SAFETY MONITORING

In compliance with the Washington University Institutional Data and Safety Monitoring Plan, the Principal Investigator will provide a Data and Safety Monitoring (DSM) report to the Washington University Quality Assurance and Safety Monitoring Committee (QASMC) semi-annually beginning six months after accrual has opened (if at least one patient has been enrolled) or one year after accrual has opened (if no patients have been enrolled at the six-month mark).

The Principal Investigator will review all patient data at least every six months, and provide a semi-annual report to the QASMC. This report will include:

- HRPO protocol number, protocol title, Principal Investigator name, data coordinator name, regulatory coordinator name, and statistician
- Date of initial HRPO approval, date of most recent consent HRPO approval/revision, date of HRPO expiration, date of most recent QA audit, study status, and phase of study
- History of study including summary of substantive amendments; summary of accrual suspensions including start/stop dates and reason; and summary of protocol exceptions, error, or breach of confidentiality including start/stop dates and reason
- Study-wide target accrual and study-wide actual accrual
- Protocol activation date
- Average rate of accrual observed in year 1, year 2, and subsequent years
- Expected accrual end date and accrual by cohort
- Objectives of protocol with supporting data and list the number of participants who have met each objective
- Measures of efficacy
- Early stopping rules with supporting data and list the number of participants who have met the early stopping rules
- Summary of toxicities separated by cohorts
- Abstract submissions/publications
- Summary of any recent literature that may affect the safety or ethics of the study

The study principal investigator and Research Patient Coordinator will monitor for serious toxicities on an ongoing basis. Once the principal investigator or Research Patient Coordinator becomes aware of an adverse event, the AE will be reported to the HRPO and QASMC according to institutional guidelines.

